## RESEARCH DESIGN AND METHODS

**STUDY DESIGN:** Retrospective correlation study.

**PARTICIPANT IDENTIFICATION:** Patients of all races and ethnic groups are eligible for this study. Patients will be recruited from participating sites after interpretation of initial cystoscopy and/or radiological screening, but prior to performance of a second staging biopsy and/or Transurethral Resection of Bladder Tumor (TURBT) procedure per standard of care. Pre-screening of potential participants may be performed by the principal investigator or delegates under the principal investigator's direct supervision. Once all eligibility criteria are confirmed, potential participants will be offered the opportunity to participate. Potential participants will be presented with the purpose of the study and the potential risks and benefits of participation. All potential participants who are interested in participation will undergo the informed consent process privately at the time of their appointment or during a return appointment after they have an opportunity to review the consent. Participants will be considered registered to the study upon receipt of a signed informed consent statement and determination by the principal investigator post-cystoscopy procedure that sufficient tumor tissue will likely be available to allow for excess specimen to be used in the study.

Registration information will be maintained by the Principal Investigator. All participants will be assigned a unique study ID derived from the bar-coded specimen collection kit used to collect all specimens in the study. All subjects will adhere to inclusion and exclusion criteria as listed below.

**INCLUSION CRITERIA:** To be eligible for the study, patients must meet the following criteria:

1. Ability to understand and willingness to sign an informed consent and authorization for release of tissue not required for pathologic diagnosis to be used for research purposes
2.  $\geq 18$  years old at time of consent
3. Suspected muscle-invasive cancer and/or high probability of receiving neoadjuvant chemotherapy and a cystectomy

**EXCLUSION CRITERIA:** To be eligible for the study, patients must not have any of the following:

1. Women who are pregnant or breastfeeding
2. Known tumor genetics, comorbidities or other factors, which in the treating physician's professional judgement, make the patient an unlikely candidate to receive neoadjuvant chemotherapy or a cystectomy.

**METHODS:** See Appendix B for a provider workflow checklist. Patients will be identified as noted above in "Participant Identification." Patient confidentiality will be maintained during all chart reviews and data collection.

---

#### PRE-TREATMENT BIOPSY PLAN

The standard of care for newly diagnosed or recurrent transitional cell carcinoma in the bladder is pathologic confirmation by TUR-BT (TransUrethral Resection-Bladder Tumor). This is done for both tissue confirmation and staging. Typically, a tumor that is likely to be muscle invasive is usually larger and more sessile than small and papillary. The most important part of the specimen procured is the base to confirm muscle invasive disease. Often, urologist procure enough tissue to make the diagnosis without resecting the entire tumor. Hence, often times there is plenty of tissue remaining or that can be procured for testing the study hypothesis. We suggest the surgeon procure at least 80mg of fresh tissue for this study (approximately 3-4 loops) then continue the TUR for pathologic confirmation as is standard of care.

---

## BIOPSY SAMPLE COLLECTION PARAMETERS

Tumor biopsy samples will be collected using standardized specimen collection kits, each containing a unique bar code that will serve as the patient's primary study ID. Upon completion of a TURBT procedure on a consenting patient where sufficient excess tissue is available for MCT imaging (at least 80mg of excess tumor), the excess specimen will be placed in a bar coded 15mL vial containing transport medium, chilled using an ice pack provided with each collection kit, and conveyed to FedEx for next day delivery to Animated Dynamics' laboratory in Indianapolis. See Appendix B.

---

## BIOPSY SAMPLE PROCESSING AND ANALYSIS

Upon receipt of tissue, researchers at Animated Dynamics will dissect prepared samples into small pieces up to 1 mm^3 in volume. Sample pieces will be immobilized in multi-well specimen plates using agarose. Prepared plates will be imaged using MCT. After a 2-4 hour baseline period, selected anti-cancer drugs will be applied. The dynamic spectra are then acquired for at least 9 hours to evaluate dynamic response to the applied therapeutics. Samples are then removed from the MCT system, fixed, and stored at 4° C.

---

## CHEMOTHERAPY TREATMENT PLAN

**Administration and treatment schedule:** Registered participants will be treated per routine care guidelines and subject to treating physician discretion. Patients may be treated with an additional biologic agent if done within the confines of a separate clinical trial.

**General concomitant medication and support care guidelines:** Routine care guidelines should be followed at investigator discretion.

**Dose delays/modifications:** Dose adjustments for toxicity will be based on recommendations per the package insert and at the treating investigator's discretion.

**Duration of follow up:** Participants will be followed per routine care guidelines for progression.

**Criteria for removal:** Participants may withdraw from the study at any time at their own request, or they may be withdrawn at any time at the discretion of the investigator for safety, behavioral, or administrative reasons. Reasons for participant removal include: noncompliance with study procedures or follow-up procedures; participant withdrawal of consent and election to discontinue participation in the trial; any other reason which in the opinion of the investigator, would justify removing the participant from the study.

---

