## MEASUREMENT OF EFFECT - CHEMOTHERAPY

**Timing of response assessment:** In addition to a baseline scan (obtained within 35 days prior to registration), patients' response to chemotherapy will be evaluated immediately upon surgical tumor resection per routine care guidelines and according to institutional practice.

**Methods of response assessment:** Response and progression will be evaluated in this study using the new international criteria proposed by the revised RECIST guideline (version 1.1). Changes in the largest diameter (unidimensional measurement) of the tumor lesions are used in the RECIST criteria.

**Evaluable for objective response:** Only those patients who have measurable disease present at baseline, have received at least one cycle of neoadjuvant chemotherapy, and have had their disease re-evaluated upon surgical tumor resection will be considered evaluable for response. These patients will have their response classified

according to the definitions stated below. (Note: Patients who exhibit objective disease progression prior to the end of cycle 1 will also be considered evaluable.)

**Evaluable Non-Target Disease Response:** Patients who have lesions present at baseline that are evaluable but do not meet the definitions of measurable disease, have received at least one cycle of therapy, and have had their disease re-evaluated will be considered evaluable for non-target disease. The response assessment is based on the presence, absence, or unequivocal progression of the lesions.

**Measurable disease:** Measurable lesions are defined as bladder lesions that can be accurately measured in at least one dimension (longest diameter to be recorded) as  $\geq 2$  cm by cystoscopy or CT scan, MRI, or calipers by clinical exam. All tumor measurements must be recorded in millimeters (or decimal fractions of centimeters).

**Non-measurable disease:** All other lesions (or sites of disease), including small lesions (longest diameter  $< 2$  cm), are considered non-measurable disease for purposes of this study.

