## DRUG FORMULATION AND PROCUREMENT

NOTE: All therapy in this trial is standard of care. All drugs to be tested in this study are commercially available formulations procured, stored, and administered in accordance with routine care standards and institutional policy. The primary therapies that will be screened using MCT in this study will include the following list, but may be supplemented from time to time at the investigators discretion. Therapies are listed in order of descending priority, with lower priority therapies tested subject to availability of sufficient tissue quantity. When tissue quantity permits, both combination and monotherapies will be imaged using MCT.

- DDMVAC (dose-dense methotrexate, vinblastine, doxorubicin, and cisplatin)
  - Gemcitabine and cisplatin
  - CMV (cisplatin, methotrexate, and vinblastine)

**STUDY COSTS:** All non-routine care procedures including the preparation, handling, and transport of MCT specimens, MCT assay procedures, and reporting of outcome data will be paid for by the study.

**SAFETY CONSIDERATIONS:** NOTE: All procedures and therapy in this trial are standard of care. Since the study does not entail any intervention in patients' care, only adverse events related to the loss of patient confidentiality will be reported to the IRB at the time of continuing review.

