## STATISTICAL CONSIDERATIONS

**STUDY DESIGN:** This is a non-randomized, multi-arm, multi-center, feasibility study, designed to examine the feasibility of using MCT as a chemosensitivity assay among bladder cancer patients by comparing ex-vivo MCT patterns consistent with chemotherapy response and resistance to confirmed pathological response or resistance as measured by Response Evaluation Criteria in Solid Tumors (RECIST) v1.1 criteria.

**DEFINITION OF PRIMARY OUTCOME ENDPOINT:** Feasibility is defined as a high statistical correlation between MCT-predicted response, and surgically confirmed response to neoadjuvant chemotherapy.

**ANALYSIS PLAN FOR PRIMARY OBJECTIVE:** The study will be considered successful, if a majority of specimens yield interpretable MCT results, and if MCT signatures are identified which demonstrate a high statistical correlation to confirmed patient response.

**EXPLORATORY ANALYSIS:** Due to the inadequate samples size, no formal analysis is planned. Descriptive analysis of the correlation between MCT parameters and clinical outcome measures will be performed.

**DETERMINATION OF SAMPLE SIZE:** A target sample size of 500 patients was selected for initial enrollment using the investigators' previous research experience to approximate the appropriate number needed to demonstrate the feasibility of this technique. It is anticipated that only 20-30% of enrolled patients will yield specimens evaluable for response. It is estimated that it will take approximately 6-12 months to complete accrual.

**EVALUATION FOR RESPONSE:** Participants who provide a bladder tumor specimen, have received at least one cycle of chemotherapy, and have had their disease re-evaluated upon surgical resection will be considered evaluable for response.

**REPLACEMENTS:** Participants who withdraw from the study prior to having the TURBT procedure or fail to complete at least one evaluation for response will be replaced. No reported data will be included for participants who are replaced.

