## DATA AND RECORD KEEPING

**DATA COLLECTION:** Each subject will be assigned a unique study ID number once it has been determined they meet inclusion criteria. Subject outcome data will be collected using a secure web-based data collection form which will identify subjects only by their unique study ID and procedure date. Only the study investigators will have access to the list matching each subject ID to the patient's medical records, and only the PI and his immediate staff will enter follow-up data into the data collection form. The following data points will be collected for this study:

- pre-treatment clinical/ pathological description of disease
- TURBT date, location, and clinical description
- objective response, as confirmed upon surgical tumor resection,
- Neoadjuvant chemotherapy agent(s) and regimen used
- Pre and post-treatment CT scans (if available)

**RECORD KEEPING/CONFIDENTIALITY:** This information will be stored on password protected electronic systems managed by the study team. All hardcopies of study related documents will be kept in locked and secure files accessible only to the study team. The potential risk to subjects is the loss of confidentiality. To mitigate this risk, the data collection form contains no patient identifiers. As data are entered into the data collection form, the PI will create a master list that links the patient to her study identification number. This master list will be stored in a locked room in a locked cabinet with limited public access. The electronic files will be stored on a secure computer with password protection. To minimize the risk of lost confidentiality, only study investigators will have access to the list that links patient identifiers to the assigned study number. Once the patient is assigned a study identification number, that number will be used without additional patient identifiers whenever possible. All collected information will be stored electronically on an encrypted and password protected laptop.

**RISK ASSESSMENT:** This study involves only procedures and commercial therapeutic agents used in accordance with routine care practice and institutional guidelines. No increase in patient health risk is anticipated as a result of this study. There is a slight risk of loss of confidentiality of participant information. Every effort will be made to

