### 4) Outcome Data

- a) As soon as practical after cystectomy, provide:

- i) neoadjuvant chemotherapy regimen given
- ii) pre and post-chemotherapy CT studies
- iii) pathology report from cystectomy specimen, including confirmed pathological response per RECIST v1.1 (if available)

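### A biologic given in another trial is permitted but is not a listed data item, so response to chemotherapy plus biologic would be scored as response to chemotherapy

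*Protocol*

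**What the plan says.** **Permission.** The protocol's Chemotherapy Treatment Plan leaves treatment to routine care and the treating physician, and adds: "Patients may be treated with an additional biologic agent if done within the confines of a separate clinical trial".

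**Who is evaluable.** There are two definitions, and neither mentions biologics. Measurement of Effect – Chemotherapy asks for measurable baseline disease and that patients "have received at least one cycle of neoadjuvant chemotherapy, and have had their disease re-evaluated upon surgical tumor resection will be considered evaluable for response". Statistical Considerations, under Evaluation for Response, counts "Participants who provide a bladder tumor specimen, have received at least one cycle of chemotherapy, and have had their disease re-evaluated upon surgical resection".

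**What is assayed.** Drug Formulation and Procurement names DDMVAC, gemcitabine with cisplatin, and CMV. The list is open: it "may be supplemented from time to time at the investigators discretion".

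**What is recorded.** The only treatment item under Data Collection is "Neoadjuvant chemotherapy agent(s) and regimen used". Appendix B item 4 asks for "neoadjuvant chemotherapy regimen given". Neither place asks about a biologic or about enrolment in another trial.

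**Link to records.** The same section keeps a key: "Only the study investigators will have access to the list matching each subject ID to the patient's medical records".

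**What is compared.** Statistical Considerations defines feasibility as a high correlation between the response MCT predicts and the response to neoadjuvant chemotherapy confirmed at surgery.

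**The concern.** The assay predicts the effect of the drugs applied to the tissue. In a patient who also received a biologic, surgery shows the joint effect of chemotherapy and biologic. If MCT correctly calls a tumour chemotherapy-resistant and the tumour then responds because of the biologic, the comparison counts an assay error. The Project Summary gives reliable identification of ineffective therapy as the purpose of the work, so the damage falls on the call that matters most.

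An analysis plan could handle this by separating the patients concerned, but it would need a variable that the protocol's data list does not contain.

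A second effect is possible. The single-valued predictor comes from logistic regression on the MCT metrics, and success depends on identifying signatures that correlate with confirmed response. If this trial's outcomes are used for that, mislabelled outcomes would affect the signature as well as its measured accuracy.

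**Working it through.** **Step 1: follow one patient through the text.** A patient has TURBT, provides a specimen, receives chemotherapy plus a biologic in another trial, and has surgery.

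- Permitted? Yes (Chemotherapy Treatment Plan).
- Evaluable? Yes under Statistical Considerations, since the patient will "have received at least one cycle of chemotherapy" and be re-evaluated at resection. Also yes under Measurement of Effect if baseline disease was measurable.
- Biologic on the named MCT panel? No. It could be added, but nothing requires an added agent to match what the patient received.
- Biologic on the data form or outcome checklist? Not a listed item.
- Response scored as? Response to neoadjuvant chemotherapy.

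**Step 2: numbers at stake.** The target of 500 is set from experience, with no formula to reproduce. With 20-30% expected to be evaluable, 500 × 0.20 = 100 and 500 × 0.30 = 150. Each 10% of these on a biologic is 10 to 15 patients.

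**Step 3: illustrative size.** From the protocol: n = 100 (lower end of step 2), and chemotherapy response p = 20-60%, which the Project Summary gives for cancer patients generally. Assumed, with no source in the protocol:

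- uptake b = 10-20%;
- conversion c = 20-40% of chemotherapy non-responders who receive the biologic;
- assay sensitivity and specificity of 80% each, fixed in advance;
- uptake and conversion independent of the MCT result.

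Formulas:

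- Extra responders: x = n(1−p)bc, where bc runs from 0.10 × 0.20 = 0.02 to 0.20 × 0.40 = 0.08.
- Observed sensitivity = (0.8np + 0.2x) / (np + x).
- Observed NPV = 0.8(n(1−p) − x) / (0.2np + 0.8n(1−p)).

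| p | x | Sensitivity | NPV (with no biologic) |
|---|---|---|---|
| 20% | 1.6 | 16.32/21.6 = 76% | 62.72/68 = 92% (94%) |
| 20% | 6.4 | 17.28/26.4 = 65% | 58.88/68 = 87% (94%) |
| 40% | 1.2 | 32.24/41.2 = 78% | 47.04/56 = 84% (86%) |
| 40% | 4.8 | 32.96/44.8 = 74% | 44.16/56 = 79% (86%) |
| 60% | 0.8 | 48.16/60.8 = 79% | 31.36/44 = 71% (73%) |
| 60% | 3.2 | 48.64/63.2 = 77% | 29.44/44 = 67% (73%) |

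Specificity stays at 80%, because conversion removes MCT-positive and MCT-negative non-responders in proportion. The percentages do not depend on n.

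**Step 4: a second set of assumptions.** With an 85%/85% assay and 40% response, 10% uptake and 30% conversion take sensitivity from 0.85 to 0.82, NPV from 0.895 to 0.868 and the phi correlation from 0.69 to 0.67. With 30% uptake and 50% conversion they become 0.72, 0.761 and 0.58. The direction is the same.

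**Step 5: does the direction depend on independence?** Suppose instead that the biologic converts only MCT-positive non-responders. At p = 40% there are 60 × 0.2 = 12 of them. With b = 20% and c = 40%, x = 12 × 0.08 = 0.96, and sensitivity is (32 + 0.96)/(40 + 0.96) = 80.5%, slightly up. So it does.

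**The case against.** **The patients can still be found.** A reader might infer that biologic recipients could never be removed from the analysis. The protocol does not support that. The key from study ID to medical record is kept, so investigators could re-abstract charts, and a site might mention the biologic when reporting agents and regimen. What stands is narrower: the planned dataset does not require the information, and recovering it means retrospective chart work at several centres. If the other trial is blinded, the chart may not show exposure.

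**The panel is open.** A reader might also infer that MCT would never test the biologic. The supplement clause leaves that possible. It does not tie an added agent to the patient's own treatment.

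**Evaluability is read from silence.** The two definitions do not name biologic recipients, and the investigator may withdraw a participant for any reason thought to justify it. But a patient who meets the stated conditions is evaluable on the text as written, and discretionary withdrawal is not a pre-specified rule.

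**The bias need not be downward.** This stands. Step 5 shows the direction changing when the biologic acts mainly in tumours that MCT calls sensitive, and a predictor fitted to this trial's outcomes would not behave like a fixed assay.

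**The shift is small against sampling error.** At 40% response and n = 100 there are 40 responders, and the 95% half-width around 80% is 1.96 × √(0.8 × 0.2/40) ≈ 12 points, against a shift of 2-6 points. The protocol also sets no sensitivity target. This limits the weight of the point, but the shift is systematic and does not shrink with more patients.

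**Analysis sets belong in the SAP.** Largely true, and the absence of a sensitivity analysis from the protocol is no finding. The missing data item is one, because an analysis plan cannot supply it.

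**Conclusion.** The point holds in a limited form. The protocol permits an added biologic, admits these patients to the evaluable set, and lists no item that records the exposure. Followed as written, it scores response to chemotherapy plus biologic as response to neoadjuvant chemotherapy, and the planned dataset cannot identify, separate or adjust for these patients without a return to medical records.

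The size is unknown, because the protocol gives no rate of biologic use; near-zero uptake would make the effect negligible. Under the step 3 assumptions sensitivity falls from 80% to 65-76%, 74-78% or 77-79% at 20%, 40% or 60% response, and NPV falls too. The direction rests on a fixed assay and a biologic effect independent of the MCT result. The documents do not support a claim of irreversible loss or of a certain downward bias. The remedy is cheap enough to be worth making regardless.

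**What to change.** 1. Add to the list under Data Collection, and to Appendix B item 4: *concurrent biologic or investigational agent, or co-enrolment in another trial (yes/no; agent)*.
2. State in Statistical Considerations that the primary correlation is reported in patients who received only chemotherapy, or only agents that were assayed on their tissue, with the analysis including the remaining evaluable patients shown alongside.

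The cost is one form field and one sentence. The downside is a somewhat smaller primary set: 10 to 15 fewer patients for each 10% of the expected 100 to 150 who receive an unassayed biologic. What patients may receive does not change.

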## MEASUREMENT OF EFFECT - CHEMOTHERAPY

**Timing of response assessment:** In addition to a baseline scan (obtained within 35 days prior to registration), patients' response to chemotherapy will be evaluated immediately upon surgical tumor resection per routine care guidelines and according to institutional practice.

**Methods of response assessment:** Response and progression will be evaluated in this study using the new international criteria proposed by the revised RECIST guideline (version 1.1). Changes in the largest diameter (unidimensional measurement) of the tumor lesions are used in the RECIST criteria.

**Evaluable for objective response:** Only those patients who have measurable disease present at baseline, have received at least one cycle of neoadjuvant chemotherapy, and have had their disease re-evaluated upon surgical tumor resection will be considered evaluable for response. These patients will have their response classified

according to the definitions stated below. (Note: Patients who exhibit objective disease progression prior to the end of cycle 1 will also be considered evaluable.)

**Evaluable Non-Target Disease Response:** Patients who have lesions present at baseline that are evaluable but do not meet the definitions of measurable disease, have received at least one cycle of therapy, and have had their disease re-evaluated will be considered evaluable for non-target disease. The response assessment is based on the presence, absence, or unequivocal progression of the lesions.

**Measurable disease:** Measurable lesions are defined as bladder lesions that can be accurately measured in at least one dimension (longest diameter to be recorded) as  $\geq 2$  cm by cystoscopy or CT scan, MRI, or calipers by clinical exam. All tumor measurements must be recorded in millimeters (or decimal fractions of centimeters).

**Non-measurable disease:** All other lesions (or sites of disease), including small lesions (longest diameter  $< 2$  cm), are considered non-measurable disease for purposes of this study.

**Target lesions:** Any measurable bladder lesions up to a maximum of 2 lesions per bladder and 4 lesions in total, should be identified as target lesions and recorded and measured at baseline. Target lesions should be selected on the basis of their size (lesions with the longest diameter), be representative of all lesions, but in addition should be those that lend themselves to reproducible repeated measurements. It may be the case that, on occasion, the largest lesion does not lend itself to reproducible measurement in which circumstance the next largest lesion which can be measured reproducibly should be selected. A sum of the diameters (longest for non-nodal lesions, short axis for nodal lesions) for all target lesions will be calculated and reported as the baseline sum diameters. The baseline sum diameters will be used as reference to further characterize any objective tumor regression in the measurable dimension of the disease.

**Non-target lesions:** All other lesions (or sites of disease) including any measurable lesions over and above the target lesions should be identified as non-target lesions and should also be recorded at baseline. Measurements of these lesions are not required, but the presence, absence, or in rare cases unequivocal progression of each should be noted throughout follow-up.

**Methods for Evaluation of Measurable Disease:** All measurements should be taken and recorded in metric notation using a ruler or calipers. All baseline evaluations should be performed as closely as possible to the beginning of treatment and never more than 4 weeks before the beginning of the treatment.

---

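### The percent-change response rule does not require the same measuring method before and after chemotherapy, so a scan can be compared with a surgical specimen

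*Protocol*

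**What the plan says.** The protocol has no single rule for how size is measured before and after chemotherapy. The relevant text is spread over several sections.

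- **Scale.** Measurement of Effect - Chemotherapy states: "Changes in the largest diameter (unidimensional measurement) of the tumor lesions are used in the RECIST criteria". Response Criteria then sets PR at a 30% fall in the sum from baseline, and PD at a 20% rise from the smallest sum with a rise of at least 5 mm.
- **First reading.** The timing paragraph begins "In addition to a baseline scan (obtained within 35 days prior to registration". It names no modality. The definition of measurable disease accepts lesions of 2 cm or more measured "by cystoscopy or CT scan, MRI, or calipers by clinical exam".
- **Second reading.** In the same timing paragraph, "patients' response to chemotherapy will be evaluated immediately upon surgical tumor resection per routine care guidelines and according to institutional practice". No instrument is named.
- **Evaluability.** Patients who meet the other conditions and "have had their disease re-evaluated upon surgical tumor resection will be considered evaluable for response". A post-chemotherapy image is not among the conditions.
- **Data collected.** Data and Record Keeping lists response as confirmed at resection and "Pre and post-treatment CT scans (if available". Appendix B, Outcome Data, lists "pre and post-chemotherapy CT studies" without that qualifier. It also asks for the cystectomy pathology report, with the RECIST v1.1 response as part of that item where available.
- **Consistency.** The nearest text says that target lesions "should be those that lend themselves to reproducible repeated measurements".

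**The concern.** A percent change means something only if both diameters are on the same footing. Here the baseline is a scan, the response reading is placed at surgery under local practice, and the RECIST result is requested with the pathology report. A site that follows this literally can subtract a specimen measurement from an imaging measurement. Any disagreement between the two methods then counts as tumour shrinkage or growth.

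Response is the reference standard against which the MCT predictor is fitted and judged, and it is the study's only objective. Error in that standard lowers the apparent association even for a good assay. Because the method follows institutional practice, the error can also differ between sites. The analysis cannot repair this later if the method was not recorded or no matched measurement was collected.

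**Working it through.** **1. Is there a same-method rule?** The text on reproducible measurement governs which lesions to choose as targets. The instruction to use a ruler or calipers concerns how a length is recorded and fixes no modality. No other section of the protocol links the method of the second reading to that of the first. The two CT data items differ in whether the scans are conditional, and neither makes the CT pair the source of the response category.

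**2. Thresholds in millimetres** (Response Criteria). With one post-treatment reading, the smallest sum is the baseline sum, d.

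- d = 20 mm: PR at 0.30 × 20 = 6 mm fall; PD at max(0.20 × 20, 5) = max(4, 5) = 5 mm rise.
- d = 40 mm: PR at 0.30 × 40 = 12 mm fall; PD at max(0.20 × 40, 5) = 8 mm rise.

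**3. Illustration.** The protocol gives no between-method error, so there is no figure of its own to reproduce and the values below are assumptions. Suppose the true size is unchanged and the second reading minus the first is Normal with mean b (systematic offset) and standard deviation s, both in mm.

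- False PR = Φ((−0.30d − b)/s)
- False PD = 1 − Φ((max(0.20d, 5) − b)/s)

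With b = 0:

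| d | s | False PR | False PD | Total |
|---|---|---|---|---|
| 20 mm | 3 mm | Φ(−2.00) = 2.3% | 1 − Φ(1.67) = 4.8% | 7.1% |
| 20 mm | 5 mm | Φ(−1.20) = 11.5% | 1 − Φ(1.00) = 15.9% | 27.4% |
| 40 mm | 3 mm | Φ(−4.00) < 0.01% | 1 − Φ(2.67) = 0.4% | 0.4% |
| 40 mm | 5 mm | Φ(−2.40) = 0.8% | 1 − Φ(1.60) = 5.5% | 6.3% |

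A systematic offset adds to this. For d = 20 mm, b = −4 mm and s = 2 mm, false PR = Φ((−6 + 4)/2) = Φ(−1) = 15.9%. With b = +4 mm and s = 2 mm, false PD = 1 − Φ((5 − 4)/2) = 30.9%.

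**4. Same-method comparator, also assumed.** For d = 20 mm, b = 0 and s = 1 to 2 mm, false PR is at most Φ(−3) = 0.1% and false PD at most 1 − Φ(2.5) = 0.6%.

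**5. Effect on the correlation.** Suppose 40% truly respond, the assay is perfect, and a fraction f is misread in each direction. Then φ = (a − pq)/√(p(1−p)q(1−q)), with p = 0.4, a = p(1 − f) and q = a + (1 − p)f.

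- f = 0.023: a = 0.391, q = 0.405, φ = 0.95.
- f = 0.115: a = 0.354, q = 0.423, φ = 0.76.

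This applies the false-PR rate of an unchanged 20 mm lesion to every patient in both directions. It shows the direction and possible order of the loss and does not forecast it.

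**The case against.** The strongest reply is that the protocol never says a specimen diameter enters the sum. That is correct. The text gives a time and defers to local practice. A reader might infer that the plan prescribes a scan-versus-specimen comparison, but it only permits one, and Appendix B makes it plausible by placing the RECIST result with the pathology report. Likewise, the four-method list defines which lesions are measurable. It does not make cystoscopy or calipers a free choice for baseline, since the timing paragraph asks for a scan.

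A second reply is that RECIST v1.1 is adopted by reference and may carry its own same-method rule. That cannot be checked from this document. The protocol writes out its own measurability, target-lesion and response rules, includes no such rule among them, and sends the reading to surgery.

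A third reply concerns size. Someone could quote 7% to 27% as the misclassification rate. The document does not support that: the standard deviations are assumed, the lesion is the smallest that qualifies, and the total adds PD errors. If stable disease and PD both count as non-response, which the protocol does not state, only the false-PR part (2.3% to 11.5%) changes an unchanged lesion's class.

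Finally, this is a feasibility study with descriptive analysis, and its primary endpoint is pathological response at surgery. That limits the remedy. One might conclude that imaging should become the primary response or that a post-chemotherapy CT should be compulsory. The first conflicts with Specific Aims. The second conflicts with the statement under Safety Considerations that all procedures are standard of care. Appendix B asks for CT studies but does not show that every patient has them.

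**Conclusion.** The point holds as a defect in the reference standard that should be corrected. The classification rule needs two comparable diameters, and the protocol as written allows PR, stable disease and size-based PD to be assigned from readings by different methods, in a way that can vary by site. This is more than missing detail, because a site can comply fully and still produce a percent change that is not interpretable.

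The document establishes that misclassification can occur, not its rate. Under the assumed standard deviations of 3 to 5 mm with no offset, the concern is material for lesions near 2 cm and much smaller for a 40 mm sum. CR and new lesions do not depend on percent change.

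**What to change.** - Compute the RECIST percent change only from a baseline and a post-chemotherapy, pre-cystectomy measurement by the same modality, where routine care already provides the pair. Derive no percent change from the specimen.
- Record modality, date and target diameters at both times.
- Reconcile the CT item in Data and Record Keeping with the one in Appendix B, without mandating a new scan.
- Keep pathological response at surgery as the endpoint, and report it for every patient who has surgery, with or without a matched pair.

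The cost is amendment wording and a few form fields. The downside is that patients without a matched pair have no RECIST percent-change category; the protocol gives no basis for estimating how many. With 500 × 0.20 to 500 × 0.30 = 100 to 150 evaluable patients expected, that number should be reported.

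A matched pair leaves one separate problem unsolved. The baseline scan precedes registration and registration precedes TURBT, so tumour may be resected between the two measurements and counted as shrinkage.
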